## 1.0 INTRODUCTION AND HYPOTHESIS

Sickle Cell Disease (SCD) is an inherited disorder of hemoglobin that affects approximately 100,000 Americans, most of whom are from socially disadvantaged groups. Adults with SCD have a high use of health care resources, averaging more than 197,000 emergency room visits per year with almost 60,000 hospital admissions per year, and 90% of admissions for acute pain treatment. For the average individual with SCD, undiscounted medical expenses are estimated to be over \$900,000 by 45 years of age. On top of the high use of health service, approximately two thirds of adolescents and adults with SCD are receiving public health insurance.

Over the last 40 years, SCD has changed from a life-threatening disease of early childhood to a chronic disease with life-threatening vaso-occlusive episodes. With advances in health care for individuals with SCD, over 98% of children now survive into adulthood, but still face debilitating physical and psychosocial sequelae. The resulting paradigm shift has led to a large increase in adults with SCD needing chronic and preventive care with a dearth of providers equipped to care for this population

In 2014, the National Heart, Lung, and Blood Institute (NHLBI) published guidelines for evidence-based management of SCD. Mobile health (mHealth) applications (apps) for health care providers have been developed to increase the adoption of the NHLBI guidelines. Our preliminary data indicate that a lack of knowledge about SCD, is a key challenge for adults with SCD. In particular, understanding the NHLBI guidelines for the management of SCD is a major obstacle as they are not written in a manner that is understandable for individuals or family members of individuals with SCD. These findings are consistent with studies in SCD and other diseases that have found that national guidelines are written at a reading level that is too high for most patients.

In addition, many individuals with SCD and their caregivers are unsure of the best approach to use health-related technology, leading to a health care technology gap. Apps for mHealth that are patient-centered and patient-driven currently do not include evidence-based clinical guidelines. Such apps could potentially promote patient engagement and effectively close this technology gap and improve SCD-specific knowledge. Given the observation that interventions designed to increase SCD-specific knowledge can decrease health care utilization, mHealth apps with SCD-specific guidelines have the potential to improve patient outcomes.

We will develop a patient-centered mHealth app, iManage, to test the hypothesis that delivery of the NHLBI SCD-guidelines via this mHealth app will increase SCD-specific knowledge.

### 1.1 PRELIMINARY DATA

The Chronic Care Model, proposed in 1996, represents an evidence-based framework for delivery of safe, effective, cooperative, life-long care through a medical home. Based on the Chronic Care Model, we will leverage Health IT to improve SCD-specific knowledge and to directly engage and activate the patient to improve adherence to guidelines. Engaging and activating patients has been shown to improve health care outcomes.

In 2013, Koh et al. recognized that patient engagement in their own health care relies fundamentally on health literacy, or ability to obtain, process, and understand health information. Thus, they proposed augmenting the standard chronic care model with strategies to enhance health literacy and create health-literate, activated patients. The Health Literate Care Model calls for health care providers to approach all patients as if they are at risk of not understanding health information, employ a range of strategies for clear communication, and confirm patients' understanding. The

Health Literate Care Model is the foundation for developing our intervention. We will use technologies to clearly communicate knowledge and confirm their understanding of this information by testing their disease-specific knowledge. Improving SCD-specific knowledge by providing access to understandable patient-centered guidelines is an important first step in creating the informed, health-literate, activated, patient and family.

Significant evidence has described how educational materials can be used to increase health knowledge. Car et al. showed that online educational programs can significantly improve patient self-efficacy and health information evaluation skills. Educational materials also increase disease-specific knowledge in SCD. Six and twelve months after receiving an educational intervention that included family-based cognitive-behavioral and psycho-educational components, individuals with SCD had higher SCD-specific knowledge compared to those who had received no intervention. In part, we have based our intervention of mobile phone technology on the prior evidence that other technologies, including CD-ROMs and private computer networks can improve SCD-specific knowledge.

Improving SCD-specific knowledge has been shown to decrease acute health care utilization. Higher disease-specific knowledge is beneficial to adults. Increases in health knowledge—achieved through a variety of interventions, including Health IT—have been associated with improved clinical outcomes, self-efficacy, and quality of life, as well as reduced health care utilization. In a review of studies, high SCD-specific knowledge correlated with significant improvement in patients' knowledge and decrease in their depression. In addition, improvements in their ability to adapt and cope, develop more positive health beliefs, and perceive a higher quality of life were all observed, though differences did not reach statistical significance. Improvement in self-management was not measured in the studies in this review. In addition, improving SCD-specific knowledge has been shown to decrease acute health care utilization. Adapting guidelines to be patient-centered has the potential to improve SCD-specific knowledge and decrease health care utilization. However, there is a lack of technologies that deliver patient-centered educational materials about evidence-based clinical guidelines in SCD. While multiple methods have been shown to improve SCD-specific knowledge, we propose that that using a mHealth app will improve SCD-specific knowledge and could decrease acute health care utilization.

## 1.2 HYPOTHESES

Adapted mobile health applications can increase SCD-specific knowledge in adults with SCD.

## 1.3 AIMS OF THE TRIAL

**Aim 1: Integrate clinical guidelines for adults with SCD into our beta version of iManage, an mHealth app.** Three focus groups will include a total of fifteen adults with SCD to identify user needs and preferences for the guidelines and app. This information will be used to adapt iManage which will then be tested and iteratively refined through usability sessions with 10 adults until ease of use and usefulness are high.

**Aim 2: Evaluate the feasibility and acceptability of the refined iManage in a pilot study with adults with SCD.** We will recruit 50 adults from the population of adults with SCD at the Vanderbilt Meharry Sickle Cell Disease Center of Excellence and Ohio State Sickle Cell Center for a 6-month pilot study to evaluate usability, acceptance, and usage. At the end of the study, we will conduct interviews with a subset of participants to gain an in-depth understanding of usage patterns and how

to sustain engagement to promote ongoing iManage use.

**Aim 3: Evaluate the efficacy of the refined iManage app on SCD-specific knowledge.** We will test the hypothesis that the refined iManage will increase SCD-specific knowledge by measuring SCD-specific knowledge at the start and end of the 6-month pilot study. We will conduct exploratory analyses of secondary outcomes including patient activation, adherence to guidelines, missed days of school/work, and self-efficacy.

*Specific Aim 1:*

Outcomes: The primary outcome of step 1 will be themes from focus groups that will be utilized to refine the Beta version of iManage in step 2. Outcomes from step 2 will include usability data from the System Usability Score, as well as quantitative and qualitative data about task completion.

*Specific Aim 2:*

Rationale: Technological interventions can only be successful at changing outcomes if they are feasible and acceptable. Through measurement of usability, acceptance, and usage, we can discover patterns that can lead to insights about how to modify technology to have a larger impact and reach.

Outcomes: We will measure usability and acceptability of iManage through surveys at the 6 month follow up, and we will measure usage of iManage throughout the 6-month period. Usability will be measured by the widely used and validated System Usability Scale. We will measure acceptability with a validated survey instrument based on the technology acceptance model introduced by Gao et al. The mobile health application for the guidelines has built-in tracking of the number of times the application is launched, how many times each of the functions are used, and how many times each button has been pushed. To measure usage, we will record the numbers of each of these events for each adult. In addition to total use, we will measure usage over time including any use, initial use, periodic use, and sustained use. We will also use a satisfaction/acceptability questionnaire to help evaluate acceptability of the app.

*Specific Aim 3:*

Rationale: Currently, health care providers provide education about SCD at clinic visits yet, data show that technology solutions designed to improve SCD knowledge are effective. We hypothesize that delivering NHLBI SCD-guidelines via an mHealth app, iManage, will increase patients' SCD-specific knowledge

Outcomes: To test our hypothesis, we will measure the change in the primary outcome of SCD-specific knowledge between the initial visit and the 6-month follow up visit. We will measure the change in the following secondary outcomes: (1) patient activation; (2) patient and provider adherence to SCD-specific guidelines; and (3) self-efficacy. Other secondary outcomes we will assess during the pilot study period are measures from a patient-centered questionnaire, including missed days from school or work and days home in pain, barriers to care, medication adherence, PROMIS measures (Computer Adaptive Tests), PHQ-9, health literacy (through REALMSF), and acute health care utilization, specifically total emergency department (ED) visits and hospitalizations. We've elected to use all cause ED visits and hospitalizations as opposed to SCD-specific health care utilization because adults with SCD believe all-cause ED visits and hospitalization is a stronger measure of their well-being than SCD related health care utilization. We will collect ED and hospitalization data by having all participants sign information release forms during consent to track acute health care utilizations at area facilities for at least six months. Adherence to SCD guidelines: Guideline adherence is a bi-directional patient-provider interaction. We will assess whether there is documentation of recommending guidelines in the electronic medical records and see how this

compares to what patients report in iManage. Missed days from school or work: Patients will report on days missed from school or work because of illness at the 6-month follow up visit. We will also inquire about other opportunities a patient has missed because of SCD (for example missed opportunities for school or work, including having to drop out of school or work or being fired from their job). Other outcomes include SCD-specific measures of self-efficacy and patient activation, using the validated Sickle Cell Self-Efficacy Scale and the Patient Activation Measure. These instruments were validated in prior studies demonstrating rigor and reproducibility.

## 2.0 STUDY DESIGN, PHASING AND ELIGIBILITY

### 2.1 Study Design:

#### *Specific Aim 1:*

*Step 1: Understanding the needs and preferences for guidelines and iManage for adults with SCD.* Focus groups will be conducted with assistance from the [Qualitative Research Core at Vanderbilt University](#) in the format recommended by Morgan & Kruger. Focus group questions will be designed to ensure relevance and developmental appropriateness for discussion with adults. In the first half of the focus group, participants will be asked about their needs and preferences related to the guidelines (accessibility and use), and asked for feedback and suggestions for refining the iManage app. In the second half of the focus group, clinical scenarios will be presented and discussed by participants to ensure that the guidelines are actionable. These clinical scenarios will consist of real-life examples of clinic visits where guidelines could be used. The focus groups will be audio recorded using encrypted digital recorders. Interviews may also be done remotely via phone or web meeting service (such as GoToMeeting or Skype or Zoom). Audio files will then be uploaded to rev.com.

*Step 2: iManage app pilot testing.* We will employ a user-centered design approach to iteratively refine iManage for use by adults with SCD with assistance from the [Center for Research and Innovation in Systems Safety \(CRISS\)](#) at Vanderbilt or the Research Informatics Software Engineering (RISE) at Ohio State. This approach to technological design has a demonstrable track record of useful and usable designs. However, many extant medical products were designed and deployed without the benefits of user-centered design, and have led to low adoption rates, abandonment, and use errors. We will conduct two iterative development rounds of formative usability evaluations with a focus on an initial re-design of the app and further refinements after completion of the second round. We will design and employ candidate scenarios that include representative tasks that may occur during clinic visits, such as whether a patient has all of their immunizations or whether they are eligible for a certain treatment such as hydroxyurea (medication), as well as scenarios where they are likely to use the app outside of a clinic visit (e.g. to use a pain action plan for a pain episode, or to manage avascular necrosis of the hip at home). These sessions will be video recorded by a camera that mounts onto a smartphone (e.g. [name]). During each scenario, participants will be asked to “talk aloud” and prompted to talk through what they are experiencing including comments about format, content, navigation, and usability. They will be asked to voice any frustrations they are experiencing and what they like about the app. At the end of the usability session, a semi-structured interview will provide additional information about their thinking when using the app, alternative or additional functionality and opportunities for improvement. The results will include: the number and type of errors, successful completions, and qualitative comments made during and post-session. The goal of these iterative evaluations is primarily focused on if and how the participants would use iManage, and suggest any additional functionality that would be tested in future iterations.

As we have obtained feedback on our and health app, we need to adapt it based on the feedback and updated guidelines. Upon completion of this update to the app, we will want to test the usability.

These will be the same as the usability sessions in the original protocol and consent, however, we may need to recruit additional participants for the usability sessions with the updated app for 1 to 2 rounds, requiring an additional 10 participants who may need to be recruited, increasing total recruitment for this study to 85. All the usability questions, recruitment, and consent will be the same as the prior questions.

*Specific Aim 2 & 3:*

Participants will participate in two visits, an initial visit where participants will complete the surveys shown in Table 1, where the participant will be randomized into control arm or intervention arm (1:1 ratio), and if in the intervention arm, the research team will introduce and demonstrate the iManage app. At a 6-month follow up visit, surveys will be repeated, and the research team will conduct a semi-structured interview about what they liked about the mHealth app, what they didn't like, what barriers they had to using the app, how the mHealth app could be improved, and an example of when the app helped them with care of their SCD. Interviews will take place either in person or remotely via phone or web meeting service (such as GoToMeeting). When conducting remote interviews, we will record audio using software such as GoTo Meeting or Skype. All recording files will be saved to an encrypted drive, which can only be accessed by study team members. Once a file has been removed from the secured recording media and stored on the encrypted drive, it will be deleted from the recording media.

KSP trained in human subjects research will obtain consent and administer the surveys and interview. A member of the KSP will set up and instruct the participant on how to access the mHealth app on their mobile phone, how to login to the intervention using his/her unique study identifier. The KSP will provide a 10-minute demonstration of the mHealth app, and have the participant interact with the app as independently as possible for 10 minutes to complete assisted tasks to gain knowledge and confidence to take action independently. KSP will be available to assist with questions. Participants may also get emails periodically throughout the study to ask them if they have questions about the study or the guidelines.

Technology: iManage will include interactive content and a fully searchable collection of the SCD-specific guidelines that are age- and health literacy-appropriate. iManage will be a combination of a static website with guideline information and a REDCap database hosted at Vanderbilt. Through the mobile app, we will reinforce important points of guideline content; motivate patient engagement through quizzes and reminders (which may use the Twilio feature in REDCap); and facilitate peer support, for instance by forming teams to compete against each other to attain goals. These strategies were recommended by patients in a prior study. Based on aim 1, multiple updates were made to the app. In addition to the guidelines information, iManage allows participants to develop a personal profile, choose goals, report on daily symptoms, and communicate with other participants outside of the group meetings. We are attaching the terms of use document which participants will agree prior to starting the trial. No PHI will be stored on iManage or in any databases populated by iManage data. De-identified results of entered data such as daily symptoms may be shared with other participants on iManage whenever a participant uses the review results function, which shows their results and other participants de-identified results. An example of this de-identified data sharing would be seeing the average mood score of the participants as compared to themselves, which we believe should increase engagement and return of value of iManage.

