**PHASE II Pilot Feasibility Randomized Controlled Trial****(30 months)**

Fifty participants will be enrolled or a 6-month pilot study where they will be randomized to one of two arms, standard care (control arm), or receiving iManage that will include interactive content and a fully searchable collection of the SCD-specific guidelines that are age- and health literacy-appropriate (intervention arm). An equal number of participants will be in each of the two arms (25 in each arm). They will participate in an initial visit and a 6-month follow up visit.

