**3.0 EVALUATIONS****3.1 Patient Evaluations**

Participants will provide written informed consent on paper or through REDCap e-consent and sign an authorization to use or disclose personal health information (PHI) form. Participants will get a \$250 check or gift card if they are in the 4-hour focus groups and a \$100 check or gift card if they are in the 90-minute usability session. For the pilot study, they will be compensated with a \$25 gift card for their initial visit and \$50 for their 6-month follow up visit. Both visits should take about 60 minutes. All checks or gift cards will be mailed or sent electronically. During the initial visit, participants will complete surveys, and if randomized to the intervention arm, the research team will introduce and demonstrate the iManage app. At a 6-month follow up visit, surveys will be repeated, and the research team will conduct a semi-structured interview about what they liked about the mHealth app, what they didn't like, what barriers they had to using the app, how the mHealth app could be improved, and an example of when the app helped them with care of their SCD. KSP trained in human subjects research will obtain consent and administer the surveys and interview. All survey instruments will be available in electronic form (through Research Electronic Data Capture, or

REDCap) and administered via iPads. Paper forms will also be available, and KSP will be available to answer questions. The interview will be audio recorded, transcribed, and de-identified for analysis.

Table 1 Time when each activity will be completed, and time to complete each activity			
Activity or Measure	Initial visit	6-month follow up	Time (mins)
Enrollment/Consent	X		20
Demographics	X		5
Demonstration of iManage	X		20
SCD-specific knowledge	X	X	5
SCD Specific Self Efficacy Assessment 	X	X	5
Patient Reported Outcomes Measurement Information System (PROMIS) measures	X	X	10
Patient Activation Measure 	X	X	5
Adherence to guideline measurements	X	X	5
Patient-centered Outcomes Questionnaire 	X	X	5
PHQ-9	X	X	1
REALM-SF	X	X	3
Medication adherence (Visual Analogue Scale (VAS) (1 item) and modified Morisky Scale (8 items))	X	X	1
Barriers to care	X		3
iManage usage and usability Satisfaction/acceptability questionnaire (11 items)		X	10
Semi-structured interview		X	30
Compensation	\$25	\$50	

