We will measure usability and acceptability of iManage through surveys at the 6 month follow up, and we will measure usage of iManage throughout the 6-month period. Usability will be measured by the widely used and validated System Usability Scale. We will measure acceptability with a validated survey instrument based on the technology acceptance model introduced by Gao et al. The mobile health application for the guidelines has built-in tracking of the number of times the application is launched, how many times each of the functions are used, and how many times each button has been pushed. To measure usage, we will record the numbers of each of these events for each adult. In addition to total use, we will measure usage over time including any use, initial use, periodic use, and sustained use.

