### **4.3 Data Integrity, Management, and Missing Data**

This project will utilize the REDCap platform for data collection and management. Data will be manually retrieved from the EHR and entered into REDCap.

This study will utilize REDCap (Research Electronic Data Capture), a software toolset and workflow methodology for electronic collection and management of clinical and research data, to collect and store data. The OSU Center for Clinical and Translational Science (CCTS) Research Informatics Services will be used as a central location for data processing and management. REDCap provides a secure, web-based application that provides an intuitive data manipulation interface, custom reporting capabilities, audit trail functionality, real-time data monitoring/querying of participant records, and variations of data exporting/importing. REDCap is hosted by OSUWMC IT in the Ackerman Datacenter ([name]). The OSU REDCap instance is located on internal

OSUWMC network. Remote access to this network can be obtained over an encrypted VPN tunnel (AnyConnect) This VPN uses Protocol: DTLS and Cipher: RSA\_AES\_128\_SHA1. Background checks are performed on all staff that are on the network or obtaining VPN access.

We will take the following steps to ensure rigor and reproducibility of this study. Data will be de-identified, and survey responses will be securely stored in REDCap or both a password protected computer and external hard drive. A standard analysis file will be created for use in the analysis of the trial for manuscripts and reports. The analysis file will include data from screening and baseline forms, treatment forms, mHealth application data, and outcomes. First and foremost, we plan to minimize the amount of missing data through various strategies. However, in the case of missing data, randomness of missing data will be assessed and when feasible, imputation will be performed. We will minimize nonadherence and attrition by employing retention strategies and adequate follow-up of all participants (e.g. contact from study coordinator; increasing reimbursement over time for study participation). We will employ techniques to ensure self-administered survey completion by requiring needed questions in REDCap so a participant cannot submit a final survey without answering each question, and by following up on incomplete surveys through telephone contact and possibly completing the survey over the telephone.

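### Does a passing reference to group meetings, with emails assigned to no arm, leave the pilot's intervention undefined?

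*Combined protocol and SAP*

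**What the plan says.** In section 2.1 (Study Design, Specific Aim 2 & 3), the Technology paragraph lists what the app offers after its Aim 1 updates: a personal profile, goals, daily symptom reports, and the ability to "communicate with other participants outside of the group meetings". Meetings of pilot participants appear nowhere else in the document.

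The schedule is stated several times. Section 2.1 opens the pilot with "Participants will participate in two visits". Section 2.2, Phase II, says "They will participate in an initial visit and a 6-month follow up visit". Section 3.1 adds "Both visits should take about 60 minutes", and Table 1 there has one column for each of those visits.

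On contact between visits, section 2.1 says "Participants may also get emails periodically throughout the study to ask them if they have questions about the study or the guidelines". It gives no arm and no frequency.

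On records, section 3.2 counts app launches and "how many times each of the functions are used, and how many times each button has been pushed". Section 4.3 says "The analysis file will include data from screening and baseline forms, treatment forms, mHealth application data, and outcomes". The treatment forms are not described further.

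**The concern.** The definite article in the app description presupposes meetings, so a reader may suspect a part of the intervention that the protocol never describes. The emails raise a similar doubt, because they mention the guidelines and could reach either arm.

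This would matter for interpretation. Aim 3 attributes a rise in SCD-specific knowledge, the primary outcome, to delivering the guidelines through the app. Section 1.1 cites a programme without an app after which "individuals with SCD had higher SCD-specific knowledge compared to those who had received no intervention", so contact outside the app is a conceivable rival explanation. If only app users had meetings or staff contact, the comparison would be of app plus contact with standard care. If controls received guideline answers by email, and those answers raised their knowledge, the contrast would narrow. In-app tracking would show neither, and no contact log is named.

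**Working it through.** **1. The plan's own figure.** Section 4.2 states 86.2% power for a two-sided paired t-test with n = 50, mean paired difference 1.1, SD of paired differences 2.5 and alpha 0.05. The noncentrality is (1.1/2.5) × √50 = 0.44 × 7.071 = 3.11 on 49 degrees of freedom, which gives power 0.862. The figure reproduces. None of its inputs depends on meetings or emails.

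**2. Meetings against the schedule.**

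| Place | What it gives for the pilot |
|---|---|
| 2.1, opening of Aim 2 & 3 | two visits |
| 2.2, Phase II | initial visit and 6-month visit |
| 3.1, Table 1 | 15 activities in two visit columns; no meeting |
| 3.1, payment | $25 and $50, one for each visit |
| 2.1, Technology | a subordinate clause that presupposes meetings |

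The first four agree with each other and describe procedures. The fifth describes a software feature.

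**3. Could the clause mean the Aim 1 focus groups?** Not readily. Those belong to Phase I, before the modified app enters the pilot, and the recruitment total counts the groups separately: 15 focus-group + 10 usability + 50 pilot + 10 further usability = 85. The teams mentioned in the Technology paragraph are formed through the app and are not described as meeting. The clause is therefore either leftover wording or a reference to something undescribed. The text does not settle which.

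**4. Who could attend?** The sentence concerns what iManage lets its users do, and only the intervention arm receives iManage. If meetings existed, they would naturally belong to the app users' package. Nothing suggests that controls attend.

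**5. Emails.** They are optional, and they ask whether participants have questions about the study or the guidelines. They are not said to carry guideline content. The sentence follows the app set-up instructions, which points to app users, although its subject is unrestricted. It also fits the coordinator contact that section 4.3 lists as a retention measure.

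**6. Can a size be attached?** Suppose a share s of the planned 1.1 points came from contact outside the app:

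- s = 10%: 0.10 × 1.1 = 0.11 points
- s = 25%: 0.25 × 1.1 = 0.275 points
- s = 50%: 0.50 × 1.1 = 0.55 points

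With 25 per arm, and the planned SD of 2.5 used as the SD of change in each arm, the between-arm standard error is 2.5 × √(2/25) = 0.707. The 95% half-width is 2.011 × 0.707 = 1.42 points, and 0.55/0.707 = 0.78 standard errors.

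These figures do not measure the concern. Every s is an assumption. The 1.1 is a within-person change, so treating it as a between-arm difference also assumes that controls do not change. The standard error follows from 25 per arm and would be the same with no meetings or emails at all.

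**7. Consequence in each case.**

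- No meetings, no control emailed: no effect.
- Contact among app users only: the randomised comparison is valid for the app with its supporting contact, and the report describes it so.
- Question-inviting emails to both arms: the comparison is still valid, with both arms offered the same correspondence.

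No case alters the randomisation, the visits, the sample size or the analysis.

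**The case for a change.** The best argument for acting is that the repair is cheap and the ambiguity real. A feature for use outside meetings implies that meetings exist, the focus groups do not explain it, and someone repeating the trial could not tell whether the intervention included them. Answering guideline questions is a form of guideline education, and knowledge is the primary outcome. Deleting a phrase, naming the email recipients and adding a short REDCap contact form would settle the matter.

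The textual part stands: the clause does not fit the schedule, and the emails name no arm.

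The claimed harm is weaker. It depends on meetings for which this clause is the only evidence. The programme cited in section 1.1 was family-based, with cognitive-behavioural and psycho-educational components; that section does not say it was delivered in meetings and does not isolate their effect. The app already comes with a staff demonstration and support, so the intervention is in any case a package, and the trial is labelled a pilot feasibility study.

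A contact log would add description but, at 25 per arm, could not separate the effect of contact from that of the app. The undefined treatment forms might already hold such data, and the 6-month interview asks about use of the app and when it helped. The terms of use that participants accept are mentioned as an attachment but are not available here; they may describe communication between participants.

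**Conclusion.** The wording is inconsistent on a narrow point, and no change to the plan follows. The clause about meetings is best read as a clerical remnant, since every statement of procedure, the schedule table and the payments give two visits. The missing arm for the emails is a small gap: sending them to one arm or to both is defensible, and the study team will know which was done.

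The size is zero if no meetings are held and no control is emailed. Otherwise the documents support no estimate, and the consequence is how the intervention is described, not whether the comparison is valid. This rests on two assumptions: that the repeated two-visit schedule reflects what is done, and that the emails only invite questions. If meetings were in fact held among app users, ordinary reporting of what was delivered would cover them, with the result attributed to the app together with that contact.
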